5.5. CLINICAL TRIAL VISIT DESCRIPTION AND PROCEDURES

5.5.1. Visit 1 – Baseline visit

1. Explain the nature and the constraints of the clinical trial to the subject and to his/her parent(s) or guardian if the subject is under the age of 18,
2. If a female subject of childbearing potential agrees to participate to the clinical trial, make sure she is using the required method(s) of contraception,
3. Ensure the subject (and parent/guardian for subjects under the age of 18) has read, understood, dated and signed the approved Informed Consent Form (ICF),
4. Give a dated and signed copy of the ICF to each subject and parent/guardian if applicable,
5. Question the subject about demography (birthdate, race, skin phototype, gender), relevant medical history, prior therapies (stopped within 6 months of the baseline visit and that may have an impact on the inclusion/exclusion criteria) and concomitant therapies,
6. Inform subject about authorized and prohibited concomitant therapies,
7. Check inclusion/exclusion criteria (see sections 4.3 and 4.4),
8. Log into the IVR/IWR System to check the inclusion rate in terms of balance in ethnic/race background and acne severity,
9. Conduct a urine pregnancy test (UPT) for female subjects of childbearing potential,
10. Log into the eCRF to get a Subject Identification Number (SIN),
11. Perform an Investigator's Global Assessment (IGA) of the whole face (see section 7.2.1),
12. Assess the Post-Inflammatory Hyperpigmentation (PIH) severity if any (see section 7.3.1),
13. Perform the baseline Local Tolerability Assessment (erythema, scaling dryness and stinging/burning; see section),
Note: *Stinging/burning at the baseline visit should **NOT** be assessed at baseline,*
14. Take photographs of the face according to the provided procedure (subject and parent/guardian should accept through the approved ICF),
15. Question the subject about the occurrence of any adverse events (AEs) by asking an open ended question taking care not to influence the subject's answer, such as: "have you had any new symptoms, injuries, illness or side-effects or worsening of pre-existing conditions?" Record all events as appropriate on the corresponding AE eCRF pages,
16. If the subject is eligible, assign a kit number (see specific section 0) (to be reported on the prescription form),
17. Fill in a prescription form with the Subject's Identification Number,
18. The Product Dispenser (person in charge of products dispensation) will:

- a. Dispense to the subject the baseline investigational product from the adequate subject kit according to the Prescription Form,
 - b. Affix the tear-off portion of the label on the Product Dispensation Log,
 - c. Dispense to the subject the associated non-investigational products with explanations how and when to use them,
 - d. Dispense the subject participation card to the subject,
 - e. Provide appropriate verbal and written instructions on how to properly use the investigational product. The **first application** of investigational product will be conducted by the subject under the direction of the Product Dispenser **before** leaving the investigational site,
 - f. Remind the subject to not to apply the investigational product the first evening,
 - g. Dispense a subject Diary and provide verbal instruction on how to complete the Diary after each product application,
 - h. Emphasize the importance of complying with the given instructions and treatments, instruct the subject to bring back the subject's diary at the next visit,
 - i. For all female subjects, emphasize the guidelines about contraception and risks in case of pregnancy,
19. Ask the subject to complete baseline DLQI/cDLQI questionnaire,
20. Schedule the next follow up visit in two weeks \pm 1 day.

5.5.2. Visit 2 (week 2) (\pm 1 Day)

1. Question the subject about occurrence of adverse events (AEs) and record occurrence of any events and/or any changes in events that were ongoing at the previous clinical trial visit. Document all changes in the eCRF,
2. Enquire whether any concomitant therapies have been added, stopped, or changed since the subject's last visit. Document all changes in the eCRF,
3. Perform an Investigator's Global Assessment (IGA) of the whole face (see section 7.2.1).
4. Assess the Post-Inflammatory Hyperpigmentation (PIH) severity if present at baseline (see section 7.3.1),
5. Perform Local Tolerability Assessment (erythema, scaling dryness and stinging/burning; see Section 7.3.2),
6. Take photographs of the face according to the provided procedure,
7. The Product Dispenser will:
 - a. Check the returned subject's diary and interview the subject about compliance (number of missed trial product applications),

- b. Emphasize again the importance of complying with the given instructions and treatments; instruct the subject to bring back the dispensed investigational product together with the subject's diary at the next visit,
 - c. For all female subjects, emphasize the guidelines about contraception and risks in case of pregnancy,
8. Schedule the next follow up visit, visit 3 (week 8) 8 weeks after Baseline visit \pm 3 days.

5.5.3. Visit 3 (week 8) (\pm 3 Days)

1. Question the subject about occurrence of adverse events (AEs) and record occurrence of any events and/or any changes in events that were ongoing at the previous clinical trial visit. Document all changes in the eCRF,
2. Enquire whether any concomitant therapies have been added, stopped, or changed since the subject's last visit. Document all changes in the eCRF,
3. Conduct a urine pregnancy test (UPT) for female subjects of childbearing potential.
4. Perform an Investigator's Global Assessment (IGA) of the whole face (see section 7.2.1).
5. Assess the Post-Inflammatory Hyperpigmentation (PIH) severity if present at baseline (see section 7.3.1),
6. Perform Local Tolerability Assessment (erythema, scaling dryness and stinging/burning; see section 7.3.2),
7. Take photographs of the face according to the provided procedure,
8. The Product Dispenser will:
 - a. Check the returned investigational product, the subject's diary and interview the subject about compliance (number of missed trial Products applications),
 - b. Dispense from the subject kit the applicable visit treatment box,
 - c. Affix the tear-off portion of the label on the Product Dispensation Log,
 - d. Dispense to the subject the associated non-investigational clinical trial product with explanations how and when to use them,
 - e. Emphasize again the importance of complying with the given instructions and treatments; instruct the subject to bring back the subject's diary at the next visit,
 - f. For all female subjects, emphasize the guidelines about contraception and risks in case of pregnancy,
9. Schedule the next follow up Visit 4 (week 12), 12 weeks after Baseline visit \pm 3 days.

5.5.4. Visit 4 (week 12) (±3 Days)

1. Question the subject about occurrence of adverse events (AEs) and record occurrence of any events and/or any changes in events that were ongoing at the previous clinical trial visit. Document all changes in the eCRF,
2. Enquire whether any concomitant therapies have been added, stopped, or changed since the subject's last visit. Document all changes in the eCRF,
3. Conduct a urine pregnancy test (UPT) for female subjects of childbearing potential,
4. Perform an Investigator's Global Assessment (IGA) of the whole face (see section 7.2.1).
5. Evaluate Global Assessment of Improvement of acne **versus baseline** (see section 7.2.2),
6. Assess the Post-Inflammatory Hyperpigmentation (PIH) severity if present at baseline (see section 7.3.1),
7. Perform Local Tolerability Assessment (erythema, scaling dryness and stinging/burning; see Section 7.3.2),
8. Take photographs of the face according to the provided procedure,
9. The Product Dispenser will:
 - a. Check the subject's diary and interview the subject about compliance (number of missed trial products applications),
 - b. Emphasize again the importance of complying with the given instructions and treatments; instruct the subject to bring back the dispensed investigational product together with the subject's diary at the next visit,
 - c. For all female subjects, emphasize the guidelines about contraception and risks in case of pregnancy,
10. Ask the subject to complete Week 12 DLQI/cDLQI questionnaire,
11. Ask the subject to complete Subject Satisfaction questionnaire.

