1. SYNOPSIS

Clinical trial title: Subject Reported Outcome with use of Adapalene 0.3% - benzoyl peroxide 2.5% in moderate to severe acne in Dark Skin Phototype subjects		
Short title (± acronym): Subject Reported Outcome in Dark Skin Phototype subjects with acne		
Project number: 816	Clinical trial phase: IV	Clinical trial period Q1 2017 – Q4 2017
Objective(s):	The main objective of this trial is to evaluate subject reported outcomes with a fixed combination treatment containing Adapalene 0.3% - Benzoyl Peroxide (BPO) 2.5%, in the treatment of moderate to severe acne vulgaris in dark skin phototypes (IV to VI). The safety of the treatment will also be evaluated.	
Methodology:	This is a multicenter open-label, prospective trial in subjects with dark skin from one of the 3 ethnic/race backgrounds: Asian, Latin American and Black/African-American and with moderate to severe acne vulgaris on the face. All eligible subjects will receive Adapalene 0.3% - BPO 2.5% gel (Epiduo® Forte/TactuPump™ Forte) once daily on whole face. One third of subjects should have dark skin with Asian ethnic/race background. One third of subjects should have dark skin with Latin American ethnic/race background. One third of subjects should have dark skin with Black/African-American ethnic/race background In each ethnic/race backgrounds at least one third of subjects should have “Severe acne” severity (IGA 4) and two third “Moderate acne” severity (IGA 3).	
Total number of planned subjects:	Approximately 60 subjects will be enrolled	
Total number of planned sites:	4 sites	
Approximate number of subjects/site:	Approximately 10 to 20 subjects per site	
Country(ies) involved:	Mauritius, Singapore and USA	
Population and main inclusion criteria:	Male or female subjects with moderate to severe acne vulgaris, aged at least 12 years old inclusive with dark skin phototypes IV to VI meeting specific inclusion/ exclusion criteria.	
Clinical trial duration per subject	16 weeks, with 5 trial visits	
Number of visits:	Baseline, W2, W8, W12 and W16	
Investigational product:		
Name:	Epiduo® Forte / TactuPump™ Forte (CD0271 0.3% / CD1579 2.5%)	
Pharmaceutical form:	Gel	
Dose/concentration:	Adapalene 0.3% - BPO 2.5%	
Total daily dose:	4 pea-sized amounts (to cover whole face, e.g. one on the forehead, one on the chin and one on each cheek),	
Mode and frequency of administration:	Topical, once daily in the evening after washing	
Location of treated area:	Whole face	
Duration of treatment:	16 weeks	

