5.5.5. Visit 5 (week 16) (±5 Days)

1. Question the subject about occurrence of adverse events (AEs) and record occurrence of any events and/or any changes in events that were ongoing at the previous clinical trial visit. Document all changes in the eCRF,
2. Enquire whether any concomitant therapies have been added, stopped, or changed since the subject's last visit. Document all changes in the eCRF,
3. Conduct a urine pregnancy test (UPT) for female subjects of childbearing potential.
4. Perform an Investigator's Global Assessment (IGA) of the whole face (see section 7.2.1),
5. Evaluate Global Assessment of Improvement of acne **versus baseline** (see section 7.2.2),

6. Assess the Post-Inflammatory Hyperpigmentation (PIH) if present at baseline (see section 7.3.1),
7. Perform Local Tolerability Assessment (erythema, scaling dryness and stinging/burning; see Section 7.3.2),
8. Take photographs of the face according to the provided procedure,
9. The Product Dispenser will:
 - a. Check the returned investigational product, the subject's diary and interview the subject about compliance (number of missed trial Products applications),
 - b. Ensure that the subject has returned all used/unused investigational products and the subject Diary. All missing investigational product units must be documented in the Product Dispensation Log comments section and on other accountability form.
 - c. For all female subjects, reiterate the guidelines about contraception and risks in case of pregnancy during 1 month after the end of the trial.
10. Ask the subject to complete the week 16/end of the trial DLQI/cDLQI questionnaire,
11. Ask the subject to complete Subject Satisfaction and Cosmetic acceptability questionnaires,
12. Complete the Exit Form in the eCRF and give the reason for clinical trial discontinuation (see section 4.5.6).

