7. SUBJECT REPORTED OUTCOME, EFFICACY AND SAFETY ASSESSMENT

7.1. SUBJECT REPORTED OUTCOMES

The following Subject Reported Outcome (PRO) questionnaires should be filled out by the subjects. The investigator or delegate should check all questions of the PRO questionnaires for completeness prior to the subject leaving the office.

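### The main-objective questionnaires are listed after the clinical assessments at Week 12 and Week 16, and nothing in the protocol requires them earlier

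*Combined protocol and SAP*

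**What the plan says.** The Synopsis gives the subject-reported outcomes first place: "The main objective of this trial is to evaluate subject reported outcomes with a fixed combination treatment". Section 3.1 names no other purpose.

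At Week 12, section 5.5.4 lists these among the earlier steps: "Perform an Investigator's Global Assessment (IGA) of the whole face" (step 4), "Evaluate Global Assessment of Improvement of acne" against baseline (step 5) and "Perform Local Tolerability Assessment (erythema, scaling dryness and stinging/burning" (step 7). The questionnaires close the list: "Ask the subject to complete Week 12 DLQI/cDLQI questionnaire" (step 10) and "Ask the subject to complete Subject Satisfaction questionnaire" (step 11).

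At Week 16, section 5.5.5 follows the same pattern, with "Ask the subject to complete the week 16/end of the trial DLQI/cDLQI questionnaire" at step 10. The satisfaction and cosmetic questionnaires are step 11, and only the Exit Form comes after them.

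The general rule on administration, in section 7.1, is a completeness check: "The investigator or delegate should check all questions of the PRO questionnaires for completeness prior to the subject leaving the office". Section 7.1.1 fixes the timing of DLQI/cDLQI within a visit for baseline only, where it must precede application of the product. For Week 12 and Week 16, sections 7.1.1 and 7.1.2 name the visit and nothing more. The flow chart in 5.4 sets no order within a visit.

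**The concern.** A questionnaire completed at the end of a visit can pick up what happened during the visit. By then, in the listed order, the subject has been asked about adverse events, has discussed stinging and burning with the investigator, has been photographed, and has been interviewed by site staff about missed applications. At Week 12 staff also stress the importance of compliance at that point. The investigator has meanwhile examined and graded the face.

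The satisfaction questionnaire then asks about much the same matters: bother from side effects (item 1), effectiveness (item 3) and degree of improvement (item 4). If answers move in response to the visit, the trial's main results move with them. With one open-label arm and a purely descriptive analysis (6.4.1, 9.1.4), no comparison would cancel the shift.

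**Working it through.** There is no figure in the plan to reproduce and no formula applies. The check is to compare the visit lists with each other and with every section that could set an order.

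**1. Position of the questionnaires**

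| Procedure | Baseline (5.5.1) | Week 12 (5.5.4) | Week 16 (5.5.5) |
|---|---|---|---|
| Adverse-event questioning | 15 | 1 | 1 |
| IGA | 11 | 4 | 4 |
| GAI | not done | 5 | 5 |
| PIH | 12 | 6 | 6 |
| Local tolerability | 13 | 7 | 7 |
| Photographs | 14 | 8 | 8 |
| Product Dispenser's steps | 18 | 9 | 9 |
| DLQI/cDLQI | 19 | 10 | 10 |
| Satisfaction questionnaire | not done | 11 | 11 |
| Last step of the list | 20 | 11 | 12 |

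At all three visits the questionnaires are listed after the clinical assessments. Step 9 contains the compliance interview at both follow-up visits.

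**2. Is an earlier time required elsewhere?** No. Sections 5.4, 7.1, 7.1.1 and 7.1.2 do not require it, as set out above. Section 5.5.6 sends subjects who stop early to the procedures of their next theoretical visit plus the final procedures of the flow chart, again without an order.

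**3. Are the lists a strict sequence?** The baseline list cannot be.
- Eligibility is checked at step 7, but the pregnancy test is step 9 and the IGA that defines eligibility is step 11.
- The IVR/IWR log-in is step 8, but under 6.1.3 the system needs the subject identification number, which is obtained at step 10.
- DLQI/cDLQI is step 19, after the supervised first application at step 18e, although 7.1.1 requires it before application. These two passages must be reconciled.

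The follow-up lists show the same style and carry no statement that their order is binding. The supported reading is that the questionnaires are listed last and their order is otherwise uncontrolled.

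**4. Which answers are most exposed?**
- Satisfaction item 1 covers the ground of the tolerability review.
- Items 3 and 4 cover the ground of the GAI. Five of the six response labels of item 4 (excellent, good, minimal, no change, worse) are also GAI categories in 7.2.2.
- Most DLQI/cDLQI items ask about specific effects on life over the past week and are less directly exposed. DLQI item 1, on itch, soreness, pain or stinging, is closer to the tolerability discussion.

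**The case against.** The strongest reply is that position in a list is not order of performance. The baseline list proves that the numbering is not strictly chronological, and a site could give out the questionnaires on arrival without breaching the protocol. This stands, and it limits the claim. It does not remove the point: if the lists are followed, the order is unfavourable; if they are not, the order may differ between the 4 sites.

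Second, a reader might infer that subjects answer after hearing the investigator's verdict. The documents do not support that. IGA and GAI are evaluator's grades, and no section says that they are disclosed. What does involve the subject directly is the adverse-event questioning, the stinging/burning discussion and the compliance interview.

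Third, there are safeguards. Stinging/burning and adverse events are to be elicited by open, non-leading questions (7.3.2, 8.2.1), and the satisfaction form tells subjects that no answer is right or wrong and that they will not be prejudiced by it. These reduce the pressure to please but say nothing about timing.

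Fourth, the trial reference manual described in 10.1 is not among the documents and may or may not address order.

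Finally, a reader might conclude that agreement between the questionnaires and the GAI could no longer corroborate benefit. No such agreement analysis is planned (9.1.1, 9.1.4). Reordering would not make the two independent either, since both judge the same face in the same open-label trial.

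**Conclusion.** The point holds as a weakness in how the main outcome is collected, not as a demonstrated bias. The protocol lists the questionnaires after the assessments and conversations most likely to colour them, and no section visible to us puts them earlier.

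The size of any shift cannot be derived from the documents. Two stronger readings should be resisted:
- Counting forms (about 60 subjects × 2 visits × 2 questionnaires = 240, if nobody drops out) shows only how many records could be collected under this order. It does not measure harm.
- That answers would be pushed in a favourable direction is plausible, but nothing in the documents establishes it.

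The conclusion assumes that sites broadly follow the listed order, or at least are not told otherwise in the site manual. It is a free improvement: worth making because the outcome affected is the main objective and there is no control arm.

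**What to change.** State in 7.1, and reflect in the visit lists 5.5.1, 5.5.4, 5.5.5 and 5.5.6, that the questionnaires due at a visit are completed before any clinical assessment, any discussion of adverse events or tolerability, and the compliance interview.

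- **Baseline:** place DLQI/cDLQI after consent and before the clinical assessments and the first application. This reconciles step 19 with 7.1.1. It is also needed for comparability: changing only the follow-up visits would leave baseline DLQI/cDLQI listed after IGA, PIH and tolerability while follow-up DLQI/cDLQI came before them, so the before/after comparison described in 5.2 would be made under unequal conditions.
- **Completeness check (7.1):** have it done by existing site staff other than the evaluator, or by the evaluator only after IGA and GAI are recorded. Otherwise, with the questionnaires moved first, the evaluator could see the subject's answers before grading.

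The cost is a reordering of steps and a sentence in 7.1, repeated in the site manual. No procedure is added, and sample size and analysis are unchanged. Where no second staff member is at hand for the check, the second option avoids the need for one.

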5.5.5. Visit 5 (week 16) (±5 Days)

1. Question the subject about occurrence of adverse events (AEs) and record occurrence of any events and/or any changes in events that were ongoing at the previous clinical trial visit. Document all changes in the eCRF,
2. Enquire whether any concomitant therapies have been added, stopped, or changed since the subject's last visit. Document all changes in the eCRF,
3. Conduct a urine pregnancy test (UPT) for female subjects of childbearing potential.
4. Perform an Investigator's Global Assessment (IGA) of the whole face (see section 7.2.1),
5. Evaluate Global Assessment of Improvement of acne **versus baseline** (see section 7.2.2),

6. Assess the Post-Inflammatory Hyperpigmentation (PIH) if present at baseline (see section 7.3.1),
7. Perform Local Tolerability Assessment (erythema, scaling dryness and stinging/burning; see Section 7.3.2),
8. Take photographs of the face according to the provided procedure,
9. The Product Dispenser will:
 - a. Check the returned investigational product, the subject's diary and interview the subject about compliance (number of missed trial Products applications),
 - b. Ensure that the subject has returned all used/unused investigational products and the subject Diary. All missing investigational product units must be documented in the Product Dispensation Log comments section and on other accountability form.
 - c. For all female subjects, reiterate the guidelines about contraception and risks in case of pregnancy during 1 month after the end of the trial.
10. Ask the subject to complete the week 16/end of the trial DLQI/cDLQI questionnaire,
11. Ask the subject to complete Subject Satisfaction and Cosmetic acceptability questionnaires,
12. Complete the Exit Form in the eCRF and give the reason for clinical trial discontinuation (see section 4.5.6).

5.5.6. Early termination visit

In case of early termination, the procedures corresponding to the next theoretical visit should be performed (e.g. if a subject discontinues after week 2, complete the week 8 visit procedures). Additional final procedures will be conducted as indicated in the trial flow chart section 5.4.

6. CLINICAL SUPPLIES

Investigational product and supplies will be provided by the sponsor and shipped by the clinical supply unit or local depot. The investigational and non-investigational products used during this clinical trial are marketed products.

